4.4 Management of COVID-19 Positive Participant

According to the Center for Disease Control and Prevention (CDC), people with COVID-19 have had a wide range of symptoms reported – ranging from mild symptoms to severe illness. Symptoms may appear 2-14 days after exposure to the virus. Symptoms may include fever or chills, cough, shortness of breath or difficulty breathing, fatigue, muscle or body aches, headache, new loss of taste or smell, sore throat, congestion or runny nose, nausea or vomiting, diarrhea ([CDC, 2022](#)).

On screening, any participant who tests positive for SARS-CoV-2 PCR will be permitted to continue study participation. However, the Investigator will assess for the presence of any symptoms of COVID-19 and will refer the participant to their primary physician if the participant is symptomatic.

In the event that a participant seroconverts to SARS-CoV-2 between Day 1 and Day 57, the participant will be assessed as to whether any symptoms of COVID-19 had been experienced during the intervening period. This will distinguish SARS-CoV-2 infection from COVID-19 (see [Section 6.3.7](#)). Medical costs associated with COVID-19 will not

be covered by the Sponsor. The site staff will not be expected to treat participants for COVID-19 symptom management.

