6.1 Sample Size Considerations

Sample size was not calculated on a formal statistical basis; however, the sample size of 200 is large enough to illustrate diversity of user experience regarding the unsupported use of Tasso+™ for capillary blood collection.

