6.2 Randomization

Each participant will have a unique subject screening number obtained from the interactive voice response system (IVRS). Once the participant is deemed eligible, the participant will be assigned a randomization number.

Randomization will be performed via a centralized IVRS. On Day 1, eligible participants will be assigned to either Cohort A or Cohort B in a 2:1 ratio. Thus, it is planned to randomize approximately 133 participants into Cohort A and approximately 67 participants into Cohort B.

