9.5 Efficacy Analyses

9.5.1 Hypothesis Testing Strategy and Multiplicity

Hypothesis testing strategy and multiplicity are not applicable for this study.

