9.5.2.2 Testing Accuracy

Pearson's correlation coefficient will be computed to quantify the strength of the direction of the linear relationship between the venipuncture collection and the Tasso+™ collection at Day 1 for each cohort for SARS-CoV-2 serology and each chemistry analyte.

Any participant who is positive for IgG Nucleocapsid assay for either matrix (SST or EDTA), will be considered SARS-CoV-2 positive.

Contingency correlation coefficient will be computed to estimate the extent of the relationship between the venipuncture collection and the Tasso+™ collection at Day 1 for each cohort for SARS-CoV-2 serology.

This analysis will be presented for both the FAS and PPS.

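### One Pearson's r for serology, pooled over antibody-positive and antibody-negative participants, can be high with no numeric agreement among positives, and no other planned serology analysis would show this

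*SAP*

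**What the plan says.** For the primary testing-accuracy endpoint, SAP 9.5.2.2 states that "Pearson's correlation coefficient will be computed to quantify the strength of the direction of the linear relationship" between the venipuncture and Tasso+ collections, "at Day 1 for each cohort for SARS-CoV-2 serology and each chemistry analyte". Protocol 9.4.1.2 has the same analysis. Neither section splits the serology r by serostatus.

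The SAP adds a second serology statistic: "Contingency correlation coefficient will be computed to estimate the extent of the relationship" between the two collections. The only serology rule it gives is qualitative: "Any participant who is positive for IgG Nucleocapsid assay for either matrix (SST or EDTA), will be considered SARS-CoV-2 positive". Neither document says whether Pearson's r takes a numeric assay value or a coded result, or on what scale.

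Entry is not selected on antibody status. Protocol 5.1 and 5.2 contain no serology criterion, and protocol 4.4 says that "any participant who tests positive for SARS-CoV-2 PCR will be permitted to continue study participation". Seroconversion between Days 1 and 57 is a secondary endpoint, which presupposes some Day 1 negatives.

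On size, "it is planned to randomize approximately 133 participants into Cohort A and approximately 67 participants into Cohort B", and "Sample size was not calculated on a formal statistical basis". There is no target value for r, and "Hypothesis testing strategy and multiplicity are not applicable for this study".

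**The concern.** If the serology value is numeric, a group containing both positives and negatives forms two clusters. Pearson's r across the two then mixes two questions: whether Tasso+ separates positives from negatives as venous blood does, and whether it reproduces the venous value among positives. A large gap between clusters can make r high on the first question alone.

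The second question matters here. Protocol 1.2 treats these correlation coefficients as a key step towards relying on self-collected blood alone. Protocol 1.1.3 reports that in an earlier study, with a different assay on whole blood, both the positivity rate and the median antibody reading were lower with Tasso than with venous blood. A level shift is therefore a live possibility, and r cannot show one: if every Tasso+ value were exactly half the venous value, r would be 1.

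Nothing else in the plan fills the gap. The contingency coefficient addresses positive/negative association only. The one stratified accuracy analysis, SAP 9.5.4.3, is by time to laboratory receipt and covers biochemistry only. No positives-only summary, paired ratio, limits of agreement or percent agreement is planned for serology.

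**Working it through.** The plan states no correlation, target or precision, so there is no figure of its own on this point to reproduce. The only related arithmetic is the allocation: 200 × 2/3 = 133.3 and 200 × 1/3 = 66.7, which matches 133 and 67.

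**Inputs**
- Cohort sizes 133 and 67: SAP 6.2.
- Share positive, p: not given for this study. I use 0.1 to 0.9. One reference point is 27/48 = 0.563, the Day 1 positives in the earlier COVID-19 group (protocol 1.1.3; different assay and population).
- Gap d between group means in within-group SDs, the spread among positives, and the scale: not given; assumed.

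**Case 1: equal SD in both groups, zero correlation between methods inside each group**

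Covariance = p(1-p)d² and variance = p(1-p)d² + 1, in units of the within-group variance. So r = p(1-p)d² / [p(1-p)d² + 1].

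- p = 0.5, d = 6: 0.25 × 36 = 9; 9/10 = 0.90.
- p = 0.5, d = 4: 0.25 × 16 = 4; 4/5 = 0.80.
- p = 0.1 or 0.9, d = 6: 0.09 × 36 = 3.24; 3.24/4.24 = 0.76.
- p = 0.1 or 0.9, d = 4: 0.09 × 16 = 1.44; 1.44/2.44 = 0.59.
- p = 0.563: 0.20 at d = 1, 0.50 at d = 2, 0.80 at d = 4, 0.90 at d = 6.

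Because p(1-p) peaks at p = 0.5, the effect is largest there and falls symmetrically on either side. Reaching r = 0.9 from the gap alone needs d = 6.0 at p = 0.5, but d = 10 at p = 0.1 or 0.9.

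**Simulation of case 1 at the planned sizes** (3,000 runs, p = 0.563, d = 6; middle 95% of runs in brackets)

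| n | Pooled r, median | r among positives, median |
|---|---|---|
| 133 | 0.90 (0.87 to 0.92) | 0.00 (-0.23 to 0.22) |
| 67 | 0.90 (0.86 to 0.93) | 0.00 (-0.32 to 0.32) |

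**Case 2: raw scale, negatives near zero, positives with coefficient of variation CV, zero correlation among positives**

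Here r = (1-p) / [(1-p) + CV²].

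| p | CV 0.2 | CV 0.3 | CV 0.5 | CV 1.0 |
|---|---|---|---|---|
| 0.563 | 0.92 | 0.83 | 0.64 | 0.30 |
| 0.9 | 0.71 | 0.53 | 0.29 | 0.09 |

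So on a raw scale with widely varying positives, the gap alone does not give a high r.

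**Scale.** With an assumed lognormal value (medians 5 and 0.1, p = 0.563) and no correlation among positives, r is 0.63 raw and 0.94 on the log scale at CV 0.5, and 0.29 raw and 0.85 log at CV 1.0. The unstated scale alone can decide whether r looks poor or excellent.

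**If the result is coded 0/1.** Pearson's r is then phi. The contingency coefficient in its usual form is |phi|/√(1 + phi²), at most 1/√2 = 0.707 for a 2×2 table, so the two statistics carry the same information and numeric agreement among positives does not arise.

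**The case against.** The strongest objection is that the numeric read-out is not established. A reader might infer it because the SAP pairs Pearson's r with a contingency coefficient, and two statistics on the same coded result would be redundant. The documents do not support that firmly. SAP 9.5.4.3 applies the contingency coefficient to the biochemistry parameters, which are numeric, so the SAP does not reserve it for categories. Protocol 9.4.1.2 has Pearson's r alone, and every stated serology rule is positive/negative. This stands: the point is conditional on a numeric value, and the unstated variable in a primary analysis is itself something to settle.

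It can also be said that the study uses serology qualitatively, that the serology precedents cited in protocol 1.2 are overall accuracy and kappa, and that no test or threshold hangs on r. That is fair, and it limits the consequence. But if a numeric r is reported as a primary accuracy result, readers will take it as numeric agreement.

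Three stronger readings are tempting and should not be drawn:
- That the gap will in fact drive r. This depends on p, d and scale, none of which is given.
- That r rises with the share of positives. In case 1 it does so only up to p = 0.5; in case 2 it falls throughout.
- That Cohorts A and B could differ materially in r through serostatus mix. They are randomised, so only chance imbalance remains. At p = 0.5 the SD of the difference in p is √[0.25 × (1/133 + 1/67)] = 0.075. A two-SD imbalance, 0.50 against 0.35, changes r only from 0.90 to 0.89 at d = 6 and from 0.80 to 0.78 at d = 4.

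**Conclusion.** The point holds in conditional form. The serology r is pooled over serostatus. If it is computed on a numeric value, it can reach about 0.8 to 0.9 with no correlation among positives when the groups are reasonably balanced and four to six SDs apart. It is lower (0.59 at d = 4) when nine in ten share one serostatus, and can be far lower on a raw scale with a wide spread among positives. These sizes rest on assumed p, d, scale and zero within-group correlation.

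What does not depend on those assumptions is that no planned serology analysis would show a level shift or poor numeric agreement among positives. A reader might go further and conclude that the pooled r is invalid or should be replaced. The documents do not support that: it is the protocol-specified analysis and describes overall association. It needs company, not removal. This is an inexpensive improvement to a primary accuracy endpoint, not a defect that undermines the study.

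**What to change.** In SAP 9.5.2.2:

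1. State which serology variable enters Pearson's r (numeric value or coded result), on what scale, and which Tasso+ tube is paired with which venous tube.
2. Keep the all-participant r as the protocol specifies, and print the number venous-positive beside it.
3. If a numeric value is available, add by cohort and tube, among participants positive by the matching venous tube, the paired Tasso+/venous ratio analysed on the log scale, with confidence interval and limits of agreement. Give r in that group as descriptive only.
4. Add the venous-by-Tasso+ 2×2 table with positive and negative percent agreement and confidence intervals. The SAP does not currently specify this table. It is needed because restricting to venous-positives would otherwise drop participants who are venous-negative but Tasso+-positive.

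The cost is SAP wording and a small added table; no new samples are needed. If results have already been seen, label the additions as such.

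There are two downsides. First, there are fewer pairs: at p = 0.1, about 13 in Cohort A (0.1 × 133) and 7 in Cohort B (0.1 × 67), before any unusable samples, so the intervals may be wide and should be shown. Second, selecting on venous positivity restricts the range and lowers r among positives, so the ratio, not r, should be the main reading there.

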3 STUDY ENDPOINTS

3.1 Primary Endpoints

The primary endpoints that will be evaluated to assess the Tasso+™ blood collection device performance are as follows:

Sample integrity

- Percentage of overall Tasso+™/SST samples collected that are with adequate volume and without moderate or gross hemolysis on Day 1 for each cohort and on each of Days 29 and 57 for Cohorts A and B combined
- Percentage of overall Tasso+™/EDTA samples collected that are with adequate volume, without moderate or gross hemolysis, and without clotting on Day 1 for each cohort and on each of Days 29 and 57 for Cohorts A and B combined

Testing accuracy

- Correlation of SARS-CoV-2 serology between venipuncture and Tasso+™/SST or Tasso+™/EDTA samples on Day 1 for each cohort
- Correlation of each chemistry analyte between venipuncture and Tasso+™/SST samples on Day 1 for each cohort

Reliability

- Percentage of Tasso+™ device failures from Day 1 to Day 57 (see details in [Section 6.3.3](#)), defined as:
 - failure in activation of the lancet;
 - lack of any blood collection within 5 minutes;
 - incorrect attachment of the capillary collection tube to the device;
 - damage to the device or the capillary collection tube upon handling;
 - lack of maintained seal between the device and the skin surface of the participant; or
 - incomplete trigger of the button (not fully pressing the button once the Tasso+™ device is sealed to the skin surface).

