6.3.2 Testing Accuracy

Testing accuracy of the Tasso+™ device, as part of device performance, will be evaluated as (i) the correlation of SARS-CoV-2 serology between venipuncture and either Tasso+™/SST or Tasso+™/EDTA samples collected on Day 1; and (ii) the correlation of each chemistry analyte between venipuncture and Tasso+™/SST samples collected on Day 1. This endpoint will only be assessed on Day 1 for each cohort separately.

Seroconversion will be evaluated using IgG Nucleocapsid assay. A total serum (SST) or plasma (EDTA) volume of 175 µL will be necessary to cover potential retesting, if needed. Any participant who is positive for IgG Nucleocapsid assay for either matrix (SST or EDTA), will be considered SARS-CoV-2 positive.

The following chemistry analytes will be assessed for correlation between the two collection approaches (venipuncture and Tasso+™/SST) on Day 1: sodium, potassium, chloride, blood urea nitrogen, creatinine, glucose, phosphate, uric acid, and C-reactive protein.

Noteworthy, in case of long duration between sample collection and testing, there may be risks associated with inaccurate sodium, potassium, and glucose values.

If a sodium, potassium, or glucose level is determined by the PI to be possibly clinically significant, a venipuncture repeat of the test should be performed at the Investigator site for safety reasons. Testing will be performed by the Investigator site and will not be sent to the Central laboratory.

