- k Day 57 collection remotely proctor-supported, as requested (during working hours); Tasso+™ samples (SST and EDTA capillary collection tubes) to be packaged and shipped to Central Laboratory by the participant.
- L Tasso+™ samples will be tested by Central Laboratory. Assessments include (by order of priority):
 - Volume measurement (SST and EDTA capillary collection tubes), hemolysis (SST and EDTA capillary collection tubes), and evidence of clotting (EDTA capillary collection tube only).
 - Chemistry analytes (SST capillary collection tube): sodium, potassium, chloride, blood urea nitrogen, creatinine, glucose, phosphate, uric acid, and C-reactive protein.
 - Serology (SST and EDTA capillary collection tubes); any participant who is positive for IgG Nucleocapsid assay for either capillary matrix (SST or EDTA) will be considered positive.
- m Venipuncture samples will be tested by Central Laboratory. Assessments include:
 - Chemistry analytes (SST tube): sodium, potassium, chloride, blood urea nitrogen, creatinine, glucose, phosphate, uric acid, and C-reactive protein.
 - Serology (SST and EDTA tubes); any participant who is positive for IgG Nucleocapsid assay for either matrix (SST or EDTA) will be considered positive.
- n Including training for eDiary on Visit 1. Participant can report any AE in the eDiary (Symptom questionnaire). Safety data collection will be solicited from participant for the first 7 days after Tasso+™ device administration, and unsolicited AEs will be captured for the full 28-day period after each administration.

Statistical Analysis Plan (SAP)

Protocol: Phase 1 Study Evaluating Technologies for Point-of-Care Blood Collections in Support of Decentralized Outpatient Assessments in Pandemic and Clinical Trial Settings

Version Date: 27-Jun-2025

Sponsor: Resilience Government Services, Inc.

Protocol No: 5309/0024

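### SAP 9.5.2.2 sets an either-matrix-positive rule beside the primary serology coefficient and specifies no comparison by tube, so a weak Tasso+ kit can be masked

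*SAP*

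**What the plan says.** The primary endpoint in protocol 3.1, repeated in SAP 5.0, is "Correlation of SARS-CoV-2 serology between venipuncture and Tasso+™/SST or Tasso+™/EDTA samples on Day 1 for each cohort". Protocol 6.3.2 words it as "the correlation of SARS-CoV-2 serology between venipuncture and either Tasso+™/SST or Tasso+™/EDTA samples collected on Day 1".

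SAP 9.5.2.2 makes three statements about serology, in this order:

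- First comes a linear measure, given separately for the two cohorts: "Pearson's correlation coefficient will be computed to quantify the strength of the direction of the linear relationship between the venipuncture collection and the Tasso+™ collection".
- Next comes the case rule: "Any participant who is positive for IgG Nucleocapsid assay for either matrix (SST or EDTA), will be considered SARS-CoV-2 positive".
- Directly after the rule comes a categorical measure, again split by cohort: "Contingency correlation coefficient will be computed to estimate the extent of the relationship between the venipuncture collection and the Tasso+™ collection at Day 1".

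Neither statistic is specified by tube. The section does not say whether Pearson's r uses a quantitative IgG value or a result code.

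The footnotes to Table 1 in SAP 6.0 define one participant-level status on each side. For Tasso+, "any participant who is positive for IgG Nucleocapsid assay for either capillary matrix (SST or EDTA) will be considered positive". For venipuncture, "Serology (SST and EDTA tubes); any participant who is positive for IgG Nucleocapsid assay for either matrix (SST or EDTA) will be considered positive".

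The either-matrix sentence also stands in SAP 9.5.3.4 under infection surveillance. In protocol 6.3.2 it sits under Testing Accuracy, in a paragraph that opens with "Seroconversion will be evaluated using IgG Nucleocapsid assay".

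**The concern.** The either-matrix rule defines a case at participant level. That suits surveillance, where the question is whether a person has been infected. It does not suit an accuracy comparison of two kits that differ in additive and collection volume (protocol Table 2).

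If the rule feeds the accuracy table, a participant whose Tasso+/SST tube is falsely negative and whose Tasso+/EDTA tube is positive counts as full agreement with venipuncture. Someone collecting a single tube at home would learn nothing about that tube. Protocol 1.2 also wants Day 1 to show how centrifugation timing affects accuracy, and an effect confined to one matrix in Cohort A could be lost.

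Tube loss would enter the figure as well. Serology is last in the testing priority for Tasso+ samples (Table 1, footnote l), so a low-volume SST tube may have no serology result. The pooled status would then rest on EDTA alone, and the SAP has no rule for that case.

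**Working it through.** **1. Which reading does the text support?** A contingency coefficient needs categories, and the either-matrix rule is the only positive/negative definition in SAP 9.5.2.2. Protocol 9.4.1.2 contains neither the rule nor the contingency coefficient; the SAP section has both, side by side. The two Table 1 footnotes supply the two margins of a pooled 2x2 table. Where the SAP wants results by tube it says so: sample integrity (9.5.2.1), resulted analytes (9.5.4.4) and volume boxplots (9.5.4.5). Pooling is therefore the natural reading, though it is inferred from placement and not stated.

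**2. Inputs for the size.** The plan has no figure to reproduce. Cohort sizes of about 133 and 67 come from SAP 6.2. Per-tube sensitivity and specificity, prevalence and the correlation of errors are assumptions. Venipuncture is taken as truth, so pooling on the venous side changes nothing in this model.

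**3. Sensitivity.** Pooled sensitivity = 1 − P(both tubes miss), where

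P(both miss) = (1 − s1)(1 − s2) + ρ√[s1(1 − s1)s2(1 − s2)], capped at the smaller miss rate.

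| Assumed SST / EDTA | Independent misses | Greatest possible overlap |
|---|---|---|
| 85% / 85% | 97.8% | 85% |
| 90% / 90% | 99.0% | 90% |
| 95% / 95% | 99.8% | 95% |
| 95% / 70% | 98.5% | 95% |

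For 90% / 90%, independence gives 1 − 0.10 × 0.10 = 0.99. At ρ = 0.5 it is 1 − (0.01 + 0.5 × 0.09) = 0.945. Equal tubes gain nothing when all misses are shared. Unequal tubes differ: a 70% EDTA tube beside a 95% SST tube still reads 95% at the greatest overlap.

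**4. Specificity.** With independent false positives, pooled specificity is the product: 0.99² = 0.980 and 0.98² = 0.960.

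**5. The planned coefficient.** C = √[φ²/(1 + φ²)], with a maximum of 0.707 for a 2x2 table. Take sensitivities of 95% (SST) and 70% (EDTA) and independent errors:

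| Prevalence, specificity per tube | C, SST | C, EDTA | C, pooled |
|---|---|---|---|
| 40%, 100% | 0.692 | 0.607 | 0.703 |
| 20%, 98% | 0.677 | 0.600 | 0.669 |

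In the first row the pooled value is above both tubes. In the second it is below the better tube, because false positives have accumulated. In both rows the weaker tube is not visible in the pooled value.

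**6. Counts.** In Cohort A at 40% prevalence there are 133 × 0.40 = 53.2 positives. The 70% tube gives 53.2 × 0.30 = 16.0 false negatives. After pooling with independent misses, 53.2 × 0.015 = 0.8 remain. The Cohort B figures are 67 × 0.40 = 26.8 positives, 8.0 false negatives and 0.4 remaining.

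**The case against.** The strongest reply is that the SAP never says the coefficient uses the combined status. The endpoint names both kits, protocol Table 4 lists the tubes on separate rows, and SAP 9.5.4.4 treats the IgG result separately for SST and EDTA. The endpoint could be read as settling what SAP 9.5.2.2 means. The rule may also be a carry-over, since in protocol 6.3.2 it belongs to a paragraph on seroconversion. This stands as a limit on certainty. It does not remove the problem, because an analyst following SAP 9.5.2.2 is given one positive/negative definition, and it is pooled.

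A reader might infer that neither kit's serology accuracy will be shown at all. The documents do not support that. A positive/negative rule cannot combine two quantitative values, so if the IgG input is quantitative, Pearson's r could still be run for each tube. It is unspecified, not excluded.

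A reader might also infer that the reported result will be inflated. That is not supported either. Positive and negative agreement are not planned outputs, all inputs above are assumed, two tubes from one person at one visit may well share misses, and pooling can lower the coefficient.

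Sample integrity is reported by tube and cohort on Day 1 regardless, and the study is descriptive with no hypothesis test (SAP 9.5.1). Neither fact supplies serology agreement for each kit.

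**Conclusion.** The point holds as follows. SAP 9.5.2.2 puts a pooling rule next to the primary serology coefficient and specifies no serology accuracy by kit. On the natural reading, the contingency coefficient compares two pooled statuses and can hide a weak tube behind a better one.

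The size is conditional on figures that the documents do not give. With venipuncture as truth, two 90% tubes would read between 90% and 99% sensitivity, and 98% specificity per tube could fall to 96%. The direction of the effect on the coefficient is not fixed. What does not depend on these inputs is that a pooled table cannot answer an endpoint that names Tasso+/SST and Tasso+/EDTA. Clarification is needed under either reading: if comparison by tube was intended, the SAP should say so.

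**What to change.** In SAP 9.5.2.2, remove the either-matrix rule. State that Pearson's r and the contingency coefficient for serology are computed by tube and cohort, Tasso+/SST against venous SST and Tasso+/EDTA against venous EDTA, on pairs with both results. Show the 2x2 counts for each comparison and the number of Day 1 participants whose two Tasso+ tubes disagree.

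Keep the either-matrix rule for surveillance only (SAP 9.5.3.4). Make clear that the same sentence in protocol 6.3.2 defines seroconversion status and not the accuracy comparison.

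All four Day 1 serology results are already planned at the Central Laboratory, so the cost is wording and a few more tables. The downside is that the figures may look less favourable than a pooled one.
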